Subjects will be asked to provide informed consent before undergoing screening assessments to determine their eligibility to participate in the study. Consent may be collected at a visit prior to performing the assessments themselves. Screening will take place within 14 days of subjects starting a 10-day run-in period. The screening period may be extended to up to 42 days for those subjects who are undergoing wash-out from a second anti-hyperglycemic agent. During the run-in period, subjects will refrain from taking prohibited medications but will continue to take their prescribed stable dose of metformin as they will for the duration of their participation in the study. [REDACTED] may receive further training in self-injection technique if required, as determined at the screening visit. An ambulatory blood pressure monitoring (ABPM) device will be fitted and worn for 24 hours.

Following the run-in period, subjects will be admitted to the clinical unit on Day -2 and will undergo initial safety assessments and blood tests. At this time, an ABPM device will be fitted and worn for 24 hours;

[REDACTED]. Subjects will be weighed on the morning of Day -1, and further blood tests and a series of ECGs will be conducted. Subjects will eat a standardized, breakfast, lunch, and evening meal at given times without consuming any other food until the following day. Eligibility criteria will also be reverified prior to dosing. Subjects will be randomized at any time from Day -1 to prior to receiving a MEDI0382 or placebo dose on Day 1.

Each dosing period consists of 7 days of dosing and will begin on Day 1. On Day 1, dosing will begin after predose safety assessments including vital signs, blood tests, and an ECG. [REDACTED] will require a dilution by site staff prior to administration, subjects will have the option to remain as inpatients or alternatively attend the clinical unit daily for dosing and other assessments as applicable during the first two weeks. During this time, subjects will undergo supervision to self-administer the investigational product. If the subject returns on a daily basis, the visits should be at approximately the same time each day. Investigational

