product should be administered within 24 to 28 hours post the last dose. On the morning of Days 7 and 14, subjects not still residing in the clinical unit will be admitted to undergo blood samples for PK, and fitting of the ABPM device that is worn for 24 hours. On Days 8 and 15, safety assessments will be performed and an up-titration step made as per the randomization. Subjects who elect to remain as inpatients will be discharged home following completion of the Day 15 visit. Subjects will attend the clinical unit thereafter as indicated in the schedule of events.

On Day 35 subjects will be admitted to the clinic, for PK and safety assessments prior to up-titration [REDACTED] the following day, then remaining in-house for approximately 24 hours for safety and efficacy assessments. This inpatient period will be repeated on Days 42 and 49 and will include up-titration to [REDACTED]; subject to the findings of the DEC who will review 72 hours safety data at each of these dose levels. Subjects will return to the clinic following an overnight fast as an outpatient to undergo PK sampling and fitting of the ABPM device on Day 56, subject to continued dose escalation and will be discharged on the first day of the treatment extension period.

After the initial titration period to determine the HCTD, subjects will continue at the HCTD for a further 3 weeks, returning to the clinical unit at Days 7 (for an outpatient visit) and Days 20-21 (for an inpatient visit) of the treatment extension for safety and efficacy assessments and resupply of investigational product as required. A follow up visit will be performed for final safety assessments 28 days after the last dose of investigational product or as convenient in the event of discontinuation.

Subjects in Cohort 2 will follow the up-titration schedule defined by Cohort 1, with the 3-week treatment extension period being conducted at the HCTD; thus, the duration of Cohort 2 subjects' participation in the study will be determined by the results obtained from Cohort 1. Dosing in Cohort 2 will occur ≥ 7 days after initiation of Cohort 1.

TARGET SUBJECT POPULATION

Overweight or obese subjects with T2DM, aged $\geq 18 \leq 74$ years with a BMI ≥ 27 and ≤ 35 kg/m². Subjects will have a diagnosis of T2DM and inadequate blood glucose control as defined by an HbA1c of 6.5% to 8.5%, and will be on metformin monotherapy.

TREATMENT GROUPS AND REGIMENS

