1.5 Rationale for Conducting the Study

Ongoing clinical Phase 2a and 2b studies (D5670C00011 and D5670C00004) are investigating MEDI0382 doses at $\leq 300 \mu\text{g}$ for up to 24 months in subjects with T2DM. This study will evaluate the safety and tolerability of higher doses of MEDI0382 [REDACTED] than previously studied, and the impact of starting at a lower dose [REDACTED] resulting in a slower titration regimen, on the tolerability profile.

Current experience with marketed GLP-1 receptor agonists (eg, liraglutide) (Habegger et al, 2013; Henderson et al, 2016) suggests that exposure to higher doses may be associated with greater extent and durability of weight loss (Astrup et al, 2009; Davies et al, 2015). This may be particularly true of GLP1/glucagon dual receptor agonists where the glucagon agonist component is likely to drive incremental weight loss over time (Habegger et al, 2013; Henderson et al, 2016). Thus, it is anticipated that higher doses of MEDI0382 will achieve greater weight loss over a given period with the potential to impact insulin resistance and further improve glucose control. This study will explore the safety and tolerability of higher doses of MEDI0382 () to determine the highest clinically tolerated dose (HCTD), which can then be studied in future long-term efficacy studies as a potential maintenance dose.

It is also known from currently available GLP-1 monoagonists that a controlled up-titration regime is associated with improved tolerability. This study will therefore also explore the effect of starting at a lower starting dose () of MEDI0382 than has previously been studied, on tolerability, particularly in relation to GI side effects. This will allow the identification of the optimal titration regime for further exploration in future studies.

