4.8.4 Safety

4.8.4.1 Analysis of Adverse Events

Adverse events will be coded using the Medical Dictionary for Regulatory Activities (MedDRA) by system organ class (SOC) and preferred term (PT). Specific AEs will be counted once for each subject for calculating rates, but will be presented in total in subject listings. In addition, if the same AE occurs multiple times within a particular subject, the

highest severity and level of causality will be reported. If any associations of interest between AEs and baseline characteristics are observed, additional stratified results may be presented. All treatment-emergent AEs will be summarized overall and by MedDRA SOC and PT, by severity and relationship to investigational product. In addition, summaries of deaths, SAEs and treatment discontinuations due to AEs will be provided.

Additionally, the incidence and event rate of nausea and vomiting will be summarized weekly during the treatment period.

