1 INTRODUCTION

This document describes the statistical analysis methodology for protocol D5670C00030, a randomized, blinded, placebo-controlled study designed to evaluate the safety, tolerability, pharmacokinetics (PK), and efficacy of ascending doses of MEDI0382 in overweight or obese subjects with type 2 diabetes mellitus (T2DM). This document details the statistical summaries relating to each study objective and describes the general conventions and definitions that will be used. In addition, a set of table templates and specifications will be included in a statistical programming plan (SPP) to complement this document.

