3 STATISTICAL METHODS

3.1 General Considerations

Data will be presented in data listings sorted by treatment, dose, subject number, and date collected, where appropriate. Tabular summaries will be presented by treatment arm. Categorical data will be summarized by the number and percentage of subjects in each category. Continuous variables will be summarized with descriptive statistics (eg, n, mean, median, SD, minimum, and maximum).

Analyses will be conducted for each cohort and for the two cohorts combined. Formal statistical modeling analysis for the secondary efficacy endpoints will be conducted for the two-cohort combined analyses. In general, unless stated otherwise, baseline will be defined as the last value prior to dosing.

Two analyses are planned for this study as follows:

- 1 A primary analysis after the up-titration period for Cohort 2, and
- 2 A final analysis after the safety follow-up period for Cohort 2.

Data analyses will be conducted using the SAS[®] System Version 9.4 or higher (SAS Institute Inc., Cary, NC) in a UNIX platform.

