3.5.1 Adverse Events and Serious Adverse Events

Adverse events (AEs) will be coded with Medical Dictionary for Regulatory Activities (MedDRA) version 21.0 or later. Analysis of AEs will include the type, incidence, severity, and relationship to investigational product summarized by MedDRA system organ class (SOC) and preferred term (PT) by treatment group as well as overall. The AEs summarized will include only treatment-emergent AEs (TEAEs), ie, those starting after the first administration of investigational product. Subjects will be counted once for specific PT or MedDRA SOC when calculating incidence rates. If the same AE PT occurs multiple times within a subject, the highest severity and level of relationship observed will be reported. If any associations of interest between AEs and baseline characteristics are observed, additional stratified results may be presented. Non-TEAEs and serious adverse events (SAEs) will be presented in the listings.

The incidence and event rate of nausea, vomiting, and nausea/vomiting on each study day during the titration period [REDACTED] will be summarized. Note that this is not just onset of a new event but includes each day the subject experiences the event excluding the AE stop day. A similar analysis including event rates will be performed for each titration dosing periods: [REDACTED]

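### SAP 3.5.1 does not settle how a nausea or vomiting event that starts and stops on the same day is counted; applied as written, the stop-day exclusion gives it zero days

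*SAP*

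**What the plan says.** SAP 3.5.1 gives incidence and event rate for nausea, vomiting and the two combined on every study day of titration. The counting rule is: "Note that this is not just onset of a new event but includes each day the subject experiences the event excluding the AE stop day". The section then adds: "A similar analysis including event rates will be performed for each titration dosing periods". The list of those periods is redacted. No readable text in the SAP or protocol says what to do when start and stop dates coincide.

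Four other statements bear on the point:

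- SAP 1 places programming detail elsewhere: "a set of table templates and specifications will be included in a statistical programming plan (SPP) to complement this document".
- SAP 3.1 sets the levels of presentation: "Analyses will be conducted for each cohort and for the two cohorts combined".
- The protocol synopsis (Study Design) defines the periods: "Each dosing period consists of 7 days of dosing and will begin on Day 1". It also places early dose steps: "On Days 8 and 15, safety assessments will be performed and an up-titration step made as per the randomization".
- Protocol 4.8.4.1 promises that "the incidence and event rate of nausea and vomiting will be summarized weekly during the treatment period", without a day-counting rule.

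**The concern.** The sentence in SAP 3.5.1 has two halves that disagree for a same-day event. The first says that counting goes beyond onset, which implies that the onset day is counted. The second removes the stop day without qualification. When the two days are the same, one half gives a count of 1 and the other gives 0. Two programmers could each follow the SAP and produce different tables.

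The display matters because protocol 1.5 says the study explores the effect of a lower starting dose "on tolerability, particularly in relation to GI side effects". It is the planned summary that places these symptoms in time relative to each dose step. With the exclusion applied as written, a vomiting episode confined to Day 8, an up-titration day, would appear as no event on Day 8. Within an arm, the omission can only lower the displayed incidence or rate, so each arm looks better tolerated than it was. The contrast between arms could move either way, depending on which arm loses more events.

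**Working it through.** The plan gives no figure to reproduce here, so the check is of the rule itself.

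**Counted days.** Let *s* be the start day, *e* the stop day, and *D* = *e* − *s* + 1 the number of calendar days.

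- Rule as written (all event days except the stop day): *e* − *s* = *D* − 1.
- Start day always counted, stop day otherwise excluded: max(1, *D* − 1).

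| D (calendar days) | As written | Start day always counted |
|---|---|---|
| 1 | 0 | 1 |
| 2 | 1 | 1 |
| 3 | 2 | 2 |
| 4 | 3 | 3 |
| 7 | 6 | 6 |

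The two rules differ only at *D* = 1, when start and stop day are the same.

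**Dosing periods.** With 7-day periods from Day 1 (protocol synopsis), period 1 is Days 1 to 7 and period 2 is Days 8 to 14. The last two columns give the counted days, and the period if the same rule is used to assign it.

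| Event | As written | Start day always counted |
|---|---|---|
| Start Day 8, stop Day 8 | none | Day 8 (period 2) |
| Start Day 7, stop Day 8 | Day 7 (period 1) | Day 7 (period 1) |
| Start Day 7, stop Day 9 | Days 7 and 8 (periods 1 and 2) | Days 7 and 8 (periods 1 and 2) |

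**What one subject is worth.** SAP 2.4 plans 8 and 12 subjects randomized 3:1.

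- Cohort 1: 8 × 3/4 = 6 MEDI0382 and 2 placebo.
- Cohort 2: 12 × 3/4 = 9 MEDI0382 and 3 placebo.
- Combined: 15 MEDI0382 and 5 placebo.

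Take one subject whose only counted event of that term on a given day is a same-day event. As written, that subject shows as 0% instead of:

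| Display | MEDI0382 | Placebo |
|---|---|---|
| Combined | 1/15 = 6.7% | 1/5 = 20.0% |
| Cohort 1 | 1/6 = 16.7% | 1/2 = 50.0% |
| Cohort 2 | 1/9 = 11.1% | 1/3 = 33.3% |

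These percentages assume that all planned subjects are in that day's denominator, which SAP 3.5.1 does not state. They show the weight of one subject in small arms. They do not estimate the size of any undercount, which would need the share of events that start and stop on the same day.

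**The case against.** The strongest reply is that a zero count is not the natural reading. A sentence of the form *not just this, but also that* normally adds the second item to the first. Onset is counted and later days are added, so a same-day event counts once. On that reading the SAP already intends the rule proposed here. The reply adds that start-day and stop-day handling is the kind of detail a programming plan would hold, and that redactions stand close to the sentence. They stand where a titration range and a list of periods would be expected, though this cannot be confirmed.

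Part of this stands. The intended meaning may well be to count onset, and a convention may exist in the programming plan. A reader might infer that same-day events will in fact be lost; the documents do not support that, because it requires both the strict reading and no convention in the programming plan. But the exclusion is unqualified, no readable text says which half of the sentence prevails, and an exception to a rule stated in the SAP belongs beside that rule.

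The reply is also right that the consequence is limited. Overall incidence counts each subject once per preferred term or system organ class, with no stop-day rule. The display carries no test, and nothing in the documents ties dose-escalation decisions to it.

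**Conclusion.** The point holds as an unresolved conflict in the counting rule. Severity is minor and confidence moderate: the absence of a visible same-day convention is clear, but an actual undercount is not established.

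The effect is confined to same-day events in the daily titration display, and in the dosing-period analysis if the exclusion carries over. The number of affected events cannot be derived. Overall incidence by system organ class and preferred term, and the listings, are unaffected. Dropping the stop day of a multi-day event is an acceptable convention and is not in question.

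Two further inferences should be avoided. A reader might conclude that the primary safety endpoint is undercounted; it is not, because the overall incidence tables do not use this rule. A reader might also conclude that the weekly summary in protocol 4.8.4.1 is safely outside the rule. The documents do not establish that either. Dosing periods last 7 days, and SAP 3.5.1 shows no separate weekly nausea and vomiting summary, so the dosing-period analysis may be how the titration part of the weekly summary is delivered. Whether the rule reaches it is open.

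**What to change.** Add one or two sentences to SAP 3.5.1:

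- The start day of an event is always counted, including when it is also the stop day.
- For events of more than one day, the stop day remains excluded.
- Events are assigned to titration dosing periods by these same counted days.

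Check the programming plan at the same time. If it already holds a same-day convention, bring that into the SAP text so that the two agree.

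The cost is the added text and a check of the specification; no new data are needed. The downside is that a 1-day and a 2-day event both count as one day, a smaller distortion than losing the 1-day event from the display.

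### The nausea and vomiting rates by titration dosing period carry an episode into dose levels where it did not start and drop same-day events, so they can mislead in either direction

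*SAP*

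**What the plan says.** SAP 3.5.1 plans a summary of "The incidence and event rate of nausea, vomiting, and nausea/vomiting on each study day during the titration period". The counting rule follows: the count is "not just onset of a new event but includes each day the subject experiences the event", "excluding the AE stop day". The next sentence extends this to dose steps: "A similar analysis including event rates will be performed for each titration dosing periods". The list of periods after that sentence is blacked out, which is not held against the plan. The visible text gives no numerator or denominator for the period rate and no rule for an episode that crosses from one period to the next.

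The Protocol synopsis (Study Design) fixes the period length: "Each dosing period consists of 7 days of dosing and will begin on Day 1". SAP 2.2 describes weekly up-titration, so a dosing period is in general one dose level.

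Protocol 4.8.4.1 states that "the incidence and event rate of nausea and vomiting will be summarized weekly during the treatment period". It does not define event rate and has no symptomatic-day rule. The general adverse event tables in SAP 3.5.1 count a subject once per preferred term or system organ class, by treatment group and not by dose level.

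**The concern.** A count of who is symptomatic on a given day is a coherent daily prevalence. The difficulty starts when the same rule is moved to a seven-day period and reported as incidence and event rate at a dose level. A reader will take those words to mean new events arising at that dose. Under the rule, a step that causes no new nausea can show as much nausea as the step that caused it, because earlier episodes are still running. Brief events, which are plausible for vomiting, can disappear because the stop day is not counted.

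This is the only visible summary that resolves nausea and vomiting by dose. Safety and tolerability is the primary objective, and Protocol 1.5 says of the study's work on titration and gastrointestinal tolerability: "This will allow the identification of the optimal titration regime for further exploration in future studies". No onset-based summary by dosing period is visible, so a reader of the report could not undo the carry-over.

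**Working it through.** The plan states no figure to reproduce here. The sample size was set empirically, and the summary is descriptive.

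**Inputs.** From the documents: 7-day dosing periods, up to 8 weeks of up-titration, stop day not counted, 20 subjects randomised 3:1 (15 on MEDI0382, of whom 6 in Cohort 1). Assumed, because the documents give none: episode dates and durations.

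**Counting rule.** An episode with start day S and stop day E is counted on days S to E − 1, that is E − S days.

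**One illustrative episode, start Day 6, stop Day 11.** Counted days are 6 to 10: Days 6–7 in period 1 (2 days) and Days 8–10 in period 2 (3 days). With full exposure, 15 subjects give 15 × 7 = 105 subject-days per period.

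| Way of counting | Period 1 | Period 2 |
|---|---|---|
| Symptomatic days | 2 (2/105 = 1.90 per 100 subject-days) | 3 (3/105 = 2.86) |
| Episodes active in the period | 1 | 1 |
| Onsets | 1 (1/105 = 0.95) | 0 |

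In Cohort 1 alone (6 × 7 = 42 subject-days) the symptomatic-day rates are 4.76 and 7.14, against onset rates of 2.38 and 0. Under both readings of similar, period 2 is charged with an episode that began in period 1. Summing days also makes the later period look worse.

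**How often an episode crosses a step.** With onset equally likely on each of the 7 days, an episode with k counted days (k from 1 to 7) crosses into the next period with probability (k − 1)/7: 0% for k = 1, 14% for 2, 29% for 3, 57% for 5 and 86% for 7.

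**The opposite error.** If E = S, the count is E − S = 0. An event that stops the next day counts once.

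**Net effect on period incidence.** Let duration D, from start to stop day inclusive, be geometric with mean m, and let q = 1 − 1/m. Assume the same onset frequency in every period. Compare the episodes counted in period j with all onsets in a period. This equals a ratio of subject incidences if a subject has at most one episode in the period.

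- Onset in period j: counted if D ≥ 2, with probability q. Same-day episodes, a share 1/m, are lost: 33%, 20% and 12.5% for m = 3, 5, 8.
- Onset on day s of the previous period: still counted in period j if D ≥ 10 − s, with probability q^(9−s). The average over s is c = (q² + … + q⁸)/7. Each further period back multiplies this by q⁷.
- Ratio at level j = q + c × (1 + q⁷ + … + q^(7(j−2))).

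| Mean duration m | q | c | Ratio, level 1 | Ratio, level 5 | Ratio, level 8 |
|---|---|---|---|---|---|
| 3 days | 0.667 | 0.179 | 0.67 | 0.86 | 0.86 |
| 5 days | 0.800 | 0.361 | 0.80 | 1.26 | 1.26 |
| 8 days | 0.875 | 0.531 | 0.88 | 1.73 | 1.75 |

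If 70% of onsets fall in the first 3 days of a step, with the rest spread evenly over the other 4, c becomes 0.123, 0.291 and 0.467. The level 5 ratios are then 0.80, 1.17 and 1.63.

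Level 1 has no earlier period to inherit from, so its ratio is q and always below 1. Even with onsets equally frequent at every step, the first dose level would look better tolerated than the later ones.

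**The case against.** The symptomatic-day note is attached to the daily display, where it is sensible and openly stated. The period analysis is only called similar. If it counts episodes active in the period, an episode contained in one period counts once, and the multiple counting goes away. The SAP Introduction also leaves table specifications to a statistical programming plan that is not available here and may settle the matter. This stands in part: a symptomatic-day numerator at period level is an inference. Carry-over across a step remains under both readings.

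Ongoing symptoms at the current dose are also worth reporting. Onset counts alone would show nothing at a level where a subject vomited daily from an earlier onset. This stands, and it is why the symptomatic-day information should be kept under its own label.

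Three stronger readings are tempting and are not supported:

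- That the rule always inflates. A comparison restricted to counted episodes suggests so, but it drops same-day events from both sides. Against all onsets, the shortest assumed duration gives a ratio below 1.
- That the SAP contradicts an onset-based event rate in the Protocol. Protocol 4.8.4.1 does not define the term.
- That the rate could misdirect dose escalation. The escalation committee reviews cumulative safety data, and the criteria in Protocol 3.1.3.2 do not use this summary.

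**Conclusion.** The point holds as a defect of definition and dose attribution. An episode spanning an up-titration is counted at a dose level where it did not start. If days are summed, it is also counted several times. Same-day events are not counted at all. At mid to late levels, period incidence would be about 0.86, 1.26 or 1.74 times the incidence based on all onsets for mean durations of 3, 5 or 8 days (0.80, 1.17 or 1.63 with onsets concentrated early in each step).

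These figures rest on assumed geometric durations, equal onset frequency at each step and full follow-up. They show direction and rough size, and do not predict this trial's result. No hypothesis test, sample size, standard treatment-emergent adverse event table or written escalation criterion depends on the summary. The change is worth making because tolerability is the primary objective and no other visible analysis resolves nausea and vomiting by dose.

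**What to change.** In SAP 3.5.1, keep the daily display, label it daily prevalence, and count an event that starts and stops on the same day as one day. For each titration dosing period, report:

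- **(a) Event rate:** adverse event onsets in that period divided by subject-days at that dose. Each episode is counted once, at the dose level of onset, with same-day events included.
- **(b) Incidence:** subjects with at least one new onset in that period.
- **(c) Persistence:** symptom-days and subjects with ongoing symptoms, on separate labelled lines, with episodes carried over from an earlier period identified.

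Use the same definitions for the weekly summary in Protocol 4.8.4.1.

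The cost is SAP wording, a small programming change using start and stop dates already collected, and a few extra table rows. Onset counts alone do not show whether symptoms persist at the new dose, which is why line (c) stays beside them.
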